7.3 Investigational treatment

Anakinra or placebo (vehicle) dispensed in small syringes (0.67 mL) will be provided to the patient for daily subcutaneous injection. The syringes for anakinra or placebo will be undistinguishable. This will be achieved by assuring that the syringes provided by the supplier (Swedish Orphan Biovitrum, Stockholm, Sweden) are labeled only by a number or other code. If the supplier is unable to provide placebo syringes that are indistinguishable, then the pharmacist will transfer the content of each syringe into an unlabeled syringe which will then be marked in a way that neither the patient nor the physician will be able to distinguish between anakinra or placebo.

After completion of all baseline testing, patients will be given a 14-day supply of anakinra or placebo. Additional syringes from the initial batch may be given to assure that the patient has a sufficient number to last until the 14-day follow up visit, which will be scheduled within 14 ± 3 days after baseline visit. Patients will also receive instruction from the investigators regarding self-injection technique. The next set of syringes (for another 4 ± 1 weeks of treatment) will be given to the patient at the time of 14-day follow-up visit. If needed, the first 2 sets of syringes (6 ± 1 weeks) may be dispensed at the same time. A third set of syringes (for another 6 ± 1 weeks of treatment) will be given at time of the 6 weeks visit. A final set of syringes (for another 12 ± 2 weeks) will be given at the 12-week visit.

Adherence to the investigational treatment will be addressed by count of syringes and completion of all study visits. All concomitant medications will also be recorded at each clinic visit. Patients in the study will receive guidelines-based medical treatments as indicated. Such treatments may include diuretics, β -adrenergic receptor blockers, angiotensin converting enzyme inhibitors, angiotensin receptor blockers, neprilysin inhibitors, aldosterone blockers, isosorbide dinitrate, hydralazine, digoxin, ivabradine, aspirin, and statins. For such medications, we will record the start date and the daily dose, and any change in dose or suspension.

Administration of anakinra with medications that affect the immune system (i.e., immunosuppressant) or increase the risk of infection (i.e., cancer chemotherapy) is NOT permitted. If a patient requires treatment with such treatments, he/she will not be eligible for inclusion in the study. If a patient already enrolled in the study requires such treatments, the investigational treatment (anakinra or placebo) will need to be discontinued (see reason for discontinuation).

7.4 Cardiopulmonary Test

Upon completion of screening/enrollment, all subjects will be scheduled for the CPX. A physician-supervised maximal exercise test will be administered using a metabolic cart (UltimaCardioO2, MGC Diagnostics, Saint Paul, MN) that is interfaced with a treadmill. A conservative ramping treadmill protocol will be used with workload increases of 0.3 metabolic equivalents every 30-seconds. Prior to each test, the oxygen and carbon dioxide sensors will be calibrated using gases of known oxygen, nitrogen, and carbon dioxide concentrations and the flow sensor will also be calibrated using a 3-liter syringe. Subjects will then be briefed regarding the protocol and will be requested to exercise to volitional fatigue. Twelve-lead ECG monitoring will be conducted at baseline, throughout the test and into recovery. Blood pressure will be measured every two minutes using an automated exercise-compatible device (Tango M2, SunTech Medical, Morrisville, NC). In this technique, expired gases are sampled using a mouthpiece-mounted sensor, and analyzed to continuously measure oxygen (O_2) uptake; the highest 10-second average value for O_2 uptake during the final 30 seconds defines peak oxygen consumption (VO_2 peak in $mL \cdot kg^{-1} \cdot min^{-1}$). The ventilatory equivalents method will be used to determine VO_2 at the ventilatory anaerobic threshold. Ten second averaged VE and VCO_2 data, from the initiation of exercise to peak, will be input into spreadsheet software (Microsoft Excel, Microsoft Corp., Bellevue, WA) to calculate the VE/ VCO_2 slope via least squares linear regression ($y = mx + b$, m =slope). Peak Respiratory Exchange Ratio (VCO_2/VO_2) will be used for determining maximal to near maximal effort. A peak RER ≥ 1.10 is well accepted as a criterion for maximal effort and a peak RER ≥ 1.0 is considered a minimal acceptable threshold. Subjects with RER <1.0 , reflecting deconditioning as a non-cardiac cause of interruption of exercise, will be excluded. American Heart Association guidelines for exercise testing contraindications and termination criteria will be followed.

Upon completion of exercise testing, the results of the CPX will be reviewed and discussed with the patients. Patients with angina, abnormal blood pressure or heart rate response, or ECG changes suggestive of coronary ischemia will be excluded from the study.

Subjects will return to the cardiopulmonary exercise suite for the additional visits upon completion of 6 weeks (Visit 3, 42 ± 7 days) and 12 weeks (Visit 4, 84 ± 7 days) and 24 weeks (Visit 5, 168 ± 14 days) of treatment with Anakinra or placebo. At each visit, subjects will undergo a brief physical exam and repeat exercise testing. Raw data from the cardiopulmonary test will be electronically transferred, free of patient identifiers, to the Core Lab at the University of Illinois, Chicago, IL.

[figure not shown]
7.5 Doppler Echocardiogram

Prior to initiation of treatment, all subjects will undergo a transthoracic Doppler echocardiogram to measure left ventricular diastolic and systolic volumes, transmural flow Doppler spectra, mitral and tricuspidal valve annulus tissue Doppler spectra, and tricuspid annulus plane systolic excursion, and global longitudinal strain analysis, according to the recommendations of the American Society of Echocardiography. The echocardiogram will be repeated at visits 2-4. All images and loops will be acquired in an electronic format and measurements will be performed at the end of the study by 2 operators blinded to treatment allocations. The average of the two measurements will be used for measures differing $\leq 10\%$, whereas those with $>10\%$ were re-reviewed and discussed by the 2 operators resulting in a consensus.

7.6 Non-invasive hemodynamics and Bio-Impedance

The non-invasive hemodynamic assessment will be performed using an automated blood pressure cuff measurement in the arm (V100 Dinamap, GE, Boston, MA, United States) and concomitant measurements from the echocardiography. Patients will be asked to seat, with both feet flat on the floor, knees bent at 90-degree angles and hands resting on the homolateral knee for 5 minutes. Arterial elastance (E_a) is a measure of LV afterload, including both pulsatile and non-pulsatile components. E_a is defined as the negative slope of left ventricular end-systolic pressure/end-diastolic volume relationship and was calculated as left ventricular end-systolic pressure/stroke volume. LV end-systolic pressure is estimated as $0.9 \times$ brachial artery systolic blood pressure measured with an arm cuff. End-systolic elastance (E_{es}) is a measure of load-independent LV contractility and is defined as the LV end-systolic pressure-volume relationship. E_{es} is calculated as LV end-systolic pressure / LV end-systolic volume. Ventriculo-arterial coupling is defined as the ratio of E_a to E_{es} .

Non-invasive Left ventricular pressure-volume loop analysis. The loops will be constructed with data obtained non-invasively from concomitant echocardiography volume assessment and using an automated blood pressure cuff measurement in the arm (V100 Dynamap, GE, Boston, MA, United States). End-systolic pressure (ESP) is estimated as 90% of systolic pressure measured non-invasively at brachial artery. The Doppler derived E/E' value is used as a surrogate for end-diastolic pressure (EDP). The negative slope of the line connecting EDP and ESP characterize arterial elastance (E_a), a measure of afterload. The positive slope of the line connecting the pressure 0 to ESP characterizes the end-systolic elastance (E_{es}), a measure of contractility. Systolic heart failure is characterized by abnormal E_a/E_{es} coupling with increased E_a and reduced E_{es} and increased E_a/E_{es} . Measurement of changes in E_{es} , E_a and E_a/E_{es} before and after treatment, will allow to detect load-independent changes in cardiac contractility and ventriculo-arterial coupling. The pressure-volume loops allow to measure the work performed with each heart beat, as the area under the curve: the area included in the loop is the stroke work, the amount of energy used for the actual systole, whereas the area below the end-diastolic volume-pressure relationship (diastolic) and the triangular area below the E_{es} left of the ESP reflects the amount of energy used by the heart but not resulted in a systole and thus not effective. Stroke work efficiency (SWE) measures the ratio of stroke work divided by the total work and reflects a measure of efficiency of the heart.

Bioelectrical Impedance Analysis or Bio-Impedance is a non-invasive, quick and safe technique that allows estimating body composition. Impedance is briefly defined as the property of the electrical ionic conduction of soft tissue where fat and bone are considered poor conductors, however the microampere range developed during the test does not represent any hazard for the patient. The patient will be asked to stay still on the bed, with superior limbs abducted at 30° and the inferior ones at 45°. Four cutaneous electrodes (two on the foot and two on the homolateral hand) are applied. Between two electrodes, at least 5 cm distance is required. A small electricity current is applied to the electrodes. We will measure how the electricity is conducted through the body using a Quantum IV Body Composition Analyzer (JL Systems) and then, using a dedicated software, we will determine the body composition (water, lean mass and fat). The estimated duration of the study is less than 10 min.

7.7 Questionnaires

Prior to each CPX, subjects will complete the Kansas City Cardiomyopathy Questionnaire (KCCQ), the Duke Activity Status Index (DASI) questionnaires, and the Patient Health Questionnaire-9 (PHQ-9). The KCCQ is a 20-question graded questionnaire that has been extensively validated to measure impairment in quality of life in patients with HF. The questions are designed to measure a wide range of physical, emotional, social, and mental domains that contribute to overall quality of life. (Link to KCCQ through FDA website and direct access to PDF; <https://www.fda.gov/downloads/MedicalDevices/ScienceandResearch/MedicalDeviceDevelopmentTools/UCM581761.pdf> / <http://columbiaheartvalve.org/sites/default/files/PDF-Kansas-City-Questionnaire.pdf>). The DASI is a twelve-item “yes/no” questionnaire that allows for the calculation of perceived functional capacity. Each question describes a different physical activity and asks the subjects if they feel they can perform the task. The questions are weighted according to their degree of physical exertion. The weighted values from the “yes” responses are summed to produce a score in metabolic equivalents (<https://www.mdcalc.com/duke-activity-status-index-dasi>). The IPAQ-short form (IPAQ-SF) is a 7-question questionnaire that allows the estimation of daily physical activity by asking the subjects about duration and intensity of their daily physical activity. Lastly, subjects will also be asked to complete the Patient Health Questionnaire-9 (PHQ-9) (https://www.phgscreeners.com/sites/g/files/g10049256/f/201412/PHQ-9_English.pdf), a nine question standardized test which has been validated in patients with heart failure. Patients who score question 9 on the PHQ-9 as one or higher or have a total score ≥ 20 will prompt the team to alert a study team physician for patient evaluation.

7.8 Biomarkers assessment

Blood samples will be taken from a peripheral vein at time of screening, baseline visit, 2, 6, 12 and 24 weeks, and used for analysis of complete cell count with differential, comprehensive metabolic profile [including inflammatory markers] and cardiac specific biomarkers [NT-proBNP]. Testing will be performed at VCUHealth, with the exception of research-only inflammatory markers, for which the samples will be processed and stored

for single batch analysis at the end of the study. Research-only biomarkers will not be used for clinical care and will not be shared with the patient nor with the referring providers.

7.9 Study Schedule

	Screening (≤14 days from discharge)	Visit 1 (Baseline)	Visit 1.5 (14±3 days)	Visit 2 (42±7 days)	Visit 3 (84±7 days)	Visit 4 (128±14 days)
Visit location	Hospital or CRSU	CRSU	CRSU***	CRSU	CRSU	CRSU
Screening *	X					
Consent	X					
Clinical assessment **	X	X	X	X	X	X
Medication reconciliation	X	X		X	X	X
Investigational therapy dispensing		X		X	X	
CPX		X		X	X	X
Echocardiogram		X		X	X	X
Non-invasive hemodynamics/ Bio-Impedance		X		X	X	X
Safety labs (CBC, renal function)		X	X	X	X	X
Biomarkers (hsCRP, NTproBNP)		X		X	X	X

*Includes hsCRP - Pregnancy test will be performed, if indicated

**Clinical assessment includes history and physical, medication reconciliation, and assessment of adverse events

***Visit 1.5 may happen in the CRSU or in other clinics with the patient's own provider.

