Interleukin-1 Blockade in Recently Decompensated Heart Failure

A Randomized Placebo-controlled Double-blinded Study

The REDHART2 study

STUDY PROTOCOL

Principal Investigators:
[name], PhD;
[name] [name]

Virginia Commonwealth University

CHANGES TO PRIOR VERSION

Prior version dated 10-25-2018 → new version 11-13-2018

- Personnel updated in the DSMB Charter per NHLBI Liaison request (see also section 8.6, and DSMB charter);
- Modified BNP criteria to include also NT-proBNP criteria – according to the European Society of Cardiology 2016 Heart Failure Guidelines (Ponikowski P et al. Eur Heart J 2016;37:2129-2200.

Prior version dated 11-13-2018 → new version 01-23-2019

- **Section 5.2:** Addition of the IPAQ questionnaire to the quality of life assessments. It will be administered at baseline, 6, 12 and 24 weeks to assess patient perception of changes
- **Section 6.3:** Changed exclusion criteria from “prior or current malignancy” to just “current malignancy receiving targeted therapy”.
- **Section 7.1:** We clarify that the patient may need to come for additional visits between the pre-specified clinic visits for assessment and/or drug dispensing.
- **Section 7.7:** Addition of the IPAQ questionnaire to the list of study activities and clarification on when a physician will be alerted to review a participant’s chart based on questionnaire responses.
- **Section 11.3.2:** Clarification on when cases with missing CPX data will result in omission from efficacy analysis.

DSMB Charter 3.f.: Clarification of the Biostatistician as Voting Member of the DSMB.

Prior version dated 01-23-2018 → new version 03-14-2019

- **Section 5.2:** Updated echocardiography description to include 6 and 12 week ECHO timepoints
- **Sections 7.5 and 7.9:** Updated echocardiography paragraph and procedure table to include ECHOs at weeks 6 and 12
- **Section 7.8:** Removed “troponin I” from text as biomarker being tested

Prior version dated 03-14-2019 → 08-27-2019

- Section 6.3: Clarified exclusion criterion related to CRT and valve surgery ('Cardiac resynchronization therapy (CRT) during index hospitalization, or planned CRT or valve surgeries within the following 6 months').
- Section 7.9: Corrected the time window for Visit 4 to 168 ± 14 days (24 ± 2 weeks).
- Section 8.3.1: We have updated the AE section to list the most common risks related to anakinra or completion of the study procedures.

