5.1 Primary Endpoint(s)

Placebo-corrected changes in peak VO₂ at CPX after 24 weeks of treatment will be considered the primary endpoint. This will compare patients treated with anakinra (N=68) vs placebo (N=34), and provide a randomized, double-blinded assessment of the effects of IL-1 blockade on aerobic exercise performance. The data will be collected and electronically transferred to the core laboratory at the University of Illinois, Chicago, IL ([name]).

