6.4 Alternate Consent Group

The subjects who are eligible to enroll in the study but decline to participate will be asked to sign an alternate consent that allows the research team to access the electronic health record for 6 months after the enrollment and make one follow up telephone call at the end of the 6 months period if needed to ascertain vital status and incidence of new event. This alternate consent group will provide an estimate of the event rate in a group free of other research interventions.

7) STUDY DESIGN

[figure not shown]
We designed a single center, placebo-controlled, double-blinded randomized study of Anakinra in patients with recently decompensated systolic heart failure. Patients will undergo baseline clinical assessment, CPX, echocardiogram, non-invasive hemodynamics, and blood tests for biomarkers. The CPX, the echocardiogram, non-invasive hemodynamics and blood tests will be repeated at each visit (6, 12 and 24 weeks). See Schematic of Study Design.

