7.1 Clinical Assessment

A physician on the research team will conduct a thorough clinical assessment and review of the chart at time of enrollment to evaluate for all inclusion and exclusion criteria. Some of the information needed to determine eligibility may be missing, in which case additional testing would not be performed prior to consenting, and it would be completed only after the patient provided informed consent and it would be charged to the study charge account.

A clinical evaluation will also be completed at Visit 1.5 (14±3 days) to determine tolerability of the treatment and side effects, medication reconciliation and completion of a complete blood cell count with differential and basic metabolic panel.

Visits 2 (6±1 weeks), 3 (12±1 weeks) and 4 (24±2 weeks) will include a clinical safety evaluation as well as assessment of the endpoints. Additional visits may be scheduled as needed.

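### The section 7.9 schedule puts the final CPX visit at 128±14 days; sections 7.1 and 7.4 put it at days 154–182, and the two windows share no day

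*Combined protocol and SAP*

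**What the plan says.** The protocol gives the timing of the final exercise test in several places.

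- Section 7.9, schedule table, last column: "Visit 4 (128±14 days". A CPX is marked in this column.
- Section 7.1: "Visits 2 (6±1 weeks), 3 (12±1 weeks) and 4 (24±2 weeks".
- Section 7.4: "24 weeks (Visit 5, 168 ± 14 days".
- Section 7, opening paragraph: "The CPX, the echocardiogram, non-invasive hemodynamics and blood tests will be repeated at each visit (6, 12 and 24 weeks".
- Section 5.1: "Placebo-corrected changes in peak VO₂ at CPX after 24 weeks of treatment will be considered the primary endpoint".
- Section 7.3, on drug supply: "A final set of syringes (for another 12 ± 2 weeks) will be given at the 12-week visit".

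Visit labels also differ. Sections 7.1 and 7.9 number the 6-, 12- and 24-week visits 2, 3 and 4, whereas section 7.4 numbers them 3, 4 and 5. Section 7.5 relies on visit numbers alone: "The echocardiogram will be repeated at visits 2-4".

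The list of changes at the front has this entry under the 08-27-2019 version: "Section 7.9: Corrected the time window for Visit 4 to 168 ± 14 days (24 ± 2 weeks". It is context only; the conflict lies between current sections and does not depend on it.

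**The concern.** A schedule table is what staff commonly use to book visits, and section 7.10 relies on the schedule to decide which tests the study pays for. Here the table and the text give different dates for the one visit that carries the primary endpoint.

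A CPX done within the table's window would belong to neither the 12-week nor the 24-week assessment as the text defines them. Section 11 gives no rule for assigning such a test to a time point. It could be analysed as the 24-week value although measured some weeks earlier. It could instead be set aside, in which case section 11.3.2 would carry an earlier observation forward. The choice would be left to judgement.

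The visit numbering adds to the uncertainty: Visit 4 means week 24 in sections 7.1 and 7.9 but week 12 in section 7.4.

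**Working it through.** **Inputs.** Section 7.9: 14±3, 42±7, 84±7 and 128±14 days. Section 7.1: 14±3 days, then 6±1, 12±1 and 24±2 weeks. Section 7.4: 42±7, 84±7 and 168±14 days. Section 7.3: a final supply of 12±2 weeks from the 12-week visit.

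**Formulas.** Days = weeks × 7. Window = centre − half-width to centre + half-width. Two windows overlap only if the earlier one closes on or after the day the later one opens.

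**Step 1: reproduce the table's other follow-up columns.** 14/7 = 2, 42/7 = 6 and 84/7 = 12 weeks. All are whole weeks and agree with section 7.1; the 42- and 84-day columns also agree with section 7.4. The sections therefore count days from the same origin.

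**Step 2: the last column.**

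| Source | Centre | Window (days) | Window (weeks) |
|---|---|---|---|
| 7.9 | 128 | 128 − 14 = 114 to 128 + 14 = 142 | 114/7 = 16.3 to 142/7 = 20.3 |
| 7.1 | 24 × 7 = 168 | 168 − 14 = 154 to 168 + 14 = 182 | 22 to 26 |
| 7.4 | 168 | 154 to 182 | 22 to 26 |

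The table's centre is 128/7 = 18.3 weeks, the only follow-up column that is not a whole number of weeks.

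**Step 3: overlap.** 142 < 154, so there is none. The gap is 154 − 142 = 12 days, and the centres differ by 168 − 128 = 40 days.

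**Step 4: could the column be the 12-week visit, or an extra one?** The 12-week window is 84 − 7 = 77 to 84 + 7 = 91 days. The table's last window opens 114 − 91 = 23 days after that closes, so it is not the 12-week visit. Section 7 lists follow-up tests at 6, 12 and 24 weeks only, and the table has exactly three follow-up CPX columns. The last column must stand for the 24-week visit, yet its printed window does not contain day 168.

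**Step 5: corroboration from drug supply.** From day 84, 12±2 weeks is 84 + 70 = 154 to 84 + 98 = 182 days, the window in sections 7.1 and 7.4. The table's centre is only 128 − 84 = 44 days (6.3 weeks) after day 84.

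**Step 6: power.** The calculation in section 11.2 uses group sizes, the difference and the standard deviation. Visit timing does not enter it, so no stated power figure changes.

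**The case against.** The strongest reply is that the discrepancy is a single digit in a table header read from a PDF by a program. The list of changes says this window was set to 168±14 days, which fits a printed table that already reads 168 as well as it fits an edit that was missed. The documents available cannot settle this. The point stands as a reason to look at the source file first; if that reads 168, the main concern falls and only the visit numbering remains.

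Second, the endpoint's time point is not in doubt. Week 24 appears in the objective, the endpoint definition, the sample-size section and the analysis section, and nothing else supports day 128. No passage says the table overrides the text, and with a single centre there is no risk of sites reading it differently. This limits the seriousness but does not remove the contradiction in the schedule for the primary visit.

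Third, the week-24 echocardiogram is not really at risk. Section 5.2, section 7 and the 7.9 table all include it, and the visit numbers in section 7.5 agree with those in 7.1 and 7.9. Only section 7.4 departs, and it prints the weeks and days beside each label. This is accepted: the numbering is a secondary matter of consistency.

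Finally, no harm is demonstrated. That is also accepted; the documents do not show that any test was done on days 114–142.

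**Conclusion.** The concern holds. In the text as supplied, the window in section 7.9 (days 114–142) and the window in sections 7.1 and 7.4 (days 154–182) are separated by 12 days, with centres 40 days apart. A CPX booked to the table would fall at 16.3–20.3 weeks and satisfy neither the 12-week nor the 24-week window in the text.

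The contradiction itself is certain; its cause is not. The conclusion assumes that the header in the source file reads 128, and that all sections count days from the same origin, as the agreement of the 42- and 84-day columns indicates. Sample size, power and the definition of the endpoint are unaffected. It should be corrected because it concerns the primary visit and costs almost nothing to put right.

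**What to change.** 1. Compare the Visit 4 header in section 7.9 with the source file.
2. If it reads 128, reconcile it with sections 5.1, 7.1, 7.3 and 7.4 so that a single window governs the primary CPX. Which window applies is for the investigators to confirm.
3. Use one visit numbering across sections 7.1, 7.4, 7.5 and 7.9.
4. Before database lock, query the CPX dates and flag any test done on days 114–142, so that none is analysed as the 24-week value without comment. Record how any such test is handled before treatment allocation is disclosed.

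The cost is one table header, a few visit labels and one database query. No change to design, sample size or analysis model is needed.
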